During this study we will: 1) Conduct a pilot test with WWIDs (n=68) randomized to either a “Basic” or “Enhanced” intervention. Women randomized to the “Basic” group will receive general PrEP counseling from the study physician and PrEP counselor at Prevention Point, general written materials, as well as “general” reminder text messages for appointments. Those in the “Enhanced” group will receive targeted counseling by a trained PrEP counselor who will emphasize the targeted messages, doctor counseling, customized written materials, as well as supportive targeted text messages and reminders. Targeted messages and materials are informed by our formative findings. Both groups will get assistance with making their doctor appointments and will have PrEP dispensed at Prevention Point’s medical clinic. 2) To assess promise of efficacy, we will compare PrEP adherence (biomedical testing, self-report) as primary outcomes at one month, end, and three-month follow-up. We will compare changes to self-efficacy, decisional conflict, and PrEP perceptions as secondary outcomes. To assess feasibility and acceptability we will compare attitudes about the intervention, prescription pick up, and number of text messages opened. Figure 1 illustrates the study design:

Figure 1. RCT Study Design

**HIV- WWIDS
(n=68)(randomized)**

“Basic” Group

- General PrEP counseling by study physician and PrEP counselors at PPP
- General written materials on PrEP
- Assistance with medical appointments
- Prescription pick-up at PPP
- General text message reminders of appointments

“Enhanced” Group

- General PrEP counseling by study physician and targeted PrEP counseling by trained counselor
- Targeted materials based on formative findings
- Assistance with medical appointments
- Prescription pick-up at PPP
- Targeted supportive text messages and reminders

Randomized Pilot

We will recruit and enroll 68 WWIDs from syringe exchange who consent to participate in the intervention and will be randomly assigned to either the “Enhanced” or “Basic” group. Both groups will participate for six months (three months in the intervention and a three month follow-up), receiving PrEP counseling at Prevention Point (intervention monthly; control as requested by the participant), educational materials (targeted vs. general) and PrEP reminders via text messages (intervention also receives supportive messages about PrEP use). They will

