also complete surveys at the start of the study, at the one-month mark (mid intervention), the three month mark (end of intervention) and three months after the intervention is complete (follow up). Demographic information will be collected along with perceptions of PrEP, decisional conflict, and self-efficacy. Other moderators will also be collected. Compliance with PrEP will be assessed through self-report (in person and via text) and through either blood test or urine sample at one month, three months and six months. For recruitment and study timeline, see attachment A.

Study Timeline

We plan to begin the pilot RCT as soon as Institutional Review Board (IRB) approval is granted. We anticipate enrollment to take place between July through November, 2020 with follow-ups completed by March, 2021.

Inclusion/Exclusion Criteria

All participants must be self-identified women, 18 years of age or older, able to read and speak English, be HIV negative, self-report HIV risk behavior, report never taking PrEP, have a cell phone that accepts text messages, and must be a client of Prevention Point Philadelphia. They will also have to have health insurance (i.e. Medicaid). Individuals with mental illness that interferes with cognitive understanding or ability to provide informed consent will be excluded, with researchers trained to identify participants who exhibit signs of inability to meaningfully participate.

Inclusion Criteria

1. Woman-identified HIV negative client of Prevention Point Philadelphia
2. 18 of years of age or older
3. Self-report either sharing needles or having unprotected sex in the last 3 months
4. Speak and read English
5. Not have used PrEP previously
6. Have a working cell phone that receives text messages
7. Have health insurance

Recruitment

For this phase, we will recruit participants who are self-identified female clients of Prevention Point Philadelphia. Because Prevention Point received funds from the city, this protocol has also gone through review at the City of Philadelphia and been approved (see attached).

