Prevention Point Philadelphia (PPP). PPP is the only syringe exchange in Philadelphia. They promote health, empowerment and safety for communities affected by drug use and poverty by offering case management, syringe exchange, medical services, HIV and Hepatitis C (HCV) testing, addiction services, housing services, free meals, legal clinic and overdoes prevention and reversal training. PPP serves hundreds of people throughout the week, many of whom attend almost daily.

Sampling

Subjects will be screened for their interest in and eligibility for participating. We aim to enroll 68 women, assuming a 75% retention rate at the end of the intervention, leaving us a final study sample of 50. Treatment allocation will be accomplished using randomization through REDCap, a HIPAA approved research management software.

PROCEDURE PHASE 3

For graphic representation of study Procedure, see attached. Participants will be asked to participate after or while waiting for services at the study site. If they are interested, research staff will take participants into a designated private room and ask eligibility questions and be HIPAA consented. If they report that they meet the eligibility requirements, they will be taken to an HIV tester at Prevention Point Philadelphia for confirmation of status. If a woman tests positive for HIV, she will be provided regular counseling through PPP's testing program and given access to resources and services to link her to immediate care. If the woman does not have HIV and is eligible to be in the study, she will be consented into the study.

Once confirmed to be HIV-, participants will be randomized to a group using REDCap's randomization tool and a baseline survey will be conducted by research staff. All survey assessments will be orally administered to participants to address any literacy or cognitive issues. Responses will be entered into REDCap by a research staff member.

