After the baseline survey is complete, research staff will introduce the participant to the appropriate PrEP counselor. Individuals in the "Basic" group will be introduced to the current PrEP counselors at Prevention Point. Those in the "Enhanced" group will be introduced to a study counselor that will be providing the targeted messages and counseling. Initial counseling will be about PrEP and importance of adherence. The PrEP counselors will also make an appointment for the participant to meet with a doctor at Prevention Point to be assessed for whether PrEP is appropriate for the participant to take.

When the participant meets with the doctor at Prevention Point, they will use the Centers for Disease Control's diagnostic criteria for PrEP prescription (see Table 1). The doctor will not know whether the participant is in the control or intervention group. Once a participant has met with a doctor, completed testing, and is determined to be a good candidate for PrEP, their prescription will be sent to a participating pharmacy that provides medications to Prevention Point Philadelphia through their 340B clinic. 340B is a federal drug pricing program that Prevention Point Philadelphia is a member of.

Table 1. CDC Diagnostic Criteria for Prescribing PrEP

Physician will Provide at First Visit:	Physician will Provide at all visits
Assessment of possible Acute HIV infection	Assessment of HIV status
Lab screenings to determine indications (gonorrhea/chlamydia, P23+ HIV ½, RPR, HCV antibody with reflex to HCV viral load, HBV antigen and antibody, BMP for creatinine)	Assessment of side effects and advice on management

HIV risk assessment to determine PrEP indication	Assessment of adherence and counseling to support it
Medication fact sheet to patients with dosing, side effects	Assessment of STI symptoms, HIV risk behavior, counseling for risk reduction
Counseling on HIV risk reduction methods	Information on anything new regarding PrEP and respond to questions
Advice on adherence	
Advice on PrEP use with contraception and pregnancy	
Prescription for Truvada (a brand name of PrEP)	

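### Self-reported adherence, one of two unranked primary measures, is taken at follow-up by spoken interview with staff who may know the arm, so over-reporting may differ between arms

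*Combined protocol and SAP*

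**What the plan says.** **Outcome.** Study Design in the protocol states that "we will compare PrEP adherence (biomedical testing, self-report) as primary outcomes at one month, end, and three-month follow-up". Neither measure is placed above the other there, in the protocol's Analysis Plan or in the SAP.

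**Collection.** Procedure Phase 3 states that "All survey assessments will be orally administered to participants to address any literacy or cognitive issues", and then that "Responses will be entered into REDCap by a research staff member". The wording covers follow-up surveys as well as baseline. The one-month assessment is in person at the site. Study staff arrange the three-month assessment, and the plan tries to time assessments to visits the woman is already making, ideally to her counselor.

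**Who knows the arm.** Women are randomised in REDCap. After the baseline survey "research staff will introduce the participant to the appropriate PrEP counselor", and the counselor differs by arm. The only masking described is of the physician: "The doctor will not know whether the participant is in the control or intervention group".

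**Messaging by arm.** Enhanced women get weekly texts with supportive content and reminders, and a counselor who reaches out at least monthly. Basic women get bi-monthly pick-up reminders and counselor meetings at the start and for the next three weeks, then counseling only on request.

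**Other adherence data.** A blood or urine test is planned at one, three and six months. At month one each woman also texts a 1 or 0 for the previous day. Self-report is compared with blood results by ANCOVA, in the treatment group only (Primary Outcome, protocol and SAP).

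**The concern.** A woman who has missed doses must say so aloud to a member of the study team, who then types the answer. If she has been urged more often to take the medication, or if the interviewer knows she is in the arm expected to do better, she may be more inclined to claim adherence. Equal over-reporting in both arms would mainly blur a difference. Unequal over-reporting creates one.

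The self-efficacy, attitude and decisional-conflict scales are collected in the same way and have no objective counterpart. The trial is meant to judge promise of efficacy and inform a decision on a full trial, so a difference produced by reporting alone could misdirect that decision.

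**Working it through.** **Step 1: can follow-up interviewers know the arm?**
- At enrolment, yes: research staff take each woman to the counselor for her arm.
- At months one, three and six, the documents say only that research staff enter answers and study staff make contact. They do not say whether these are the same people or whether they can see the allocation.
- Restricting research assistants to de-identified data (Risk to Participants; Privacy) removes names. It is not said to hide the arm.
- The supported statement is therefore that they may know.

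**Step 2: would the plan detect unequal over-reporting?** The ANCOVA of self-report against blood result is confined to the treatment group, so it cannot show whether over-reporting differs between arms. The text item avoids a spoken answer but covers one day at one time point.

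**Step 3: sample size.** Sampling gives 68 women and 75% retention: 68 × 0.75 = 51, which the plan takes as 50, or 25 per group. The stated detectable effect of 0.79 at 80% power reproduces: (1.960 + 0.842) × √(2/25) = 0.792. So 25 per group is used below.

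**Step 4: size of the effect (illustration).** Let t be true adherence, equal in both arms, and f the share of non-adherent women who report adherence. The reported rate is r = t + (1 − t)f. The values of t and f are assumptions; the documents give none.
- t = 0.50: f = 0.10 gives 0.50 + 0.50 × 0.10 = 0.55; f = 0.30 gives 0.65; f = 0.40 gives 0.70.
- t = 0.30: f = 0.10 gives 0.30 + 0.70 × 0.10 = 0.37; f = 0.30 gives 0.51; f = 0.40 gives 0.58.

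The false-positive rate is the sum, over all pairs of counts (a, b), of Bin(a; 25, r_E) × Bin(b; 25, r_B) for pairs where the test rejects at two-sided 5%. The plan does not state sidedness. The uncorrected chi-square rejects when (a/25 − b/25)² / [p(1 − p)(2/25)] > 3.841, with p = (a + b)/50. Fisher's exact test is shown as well because the plan allows it.

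| True adherence | Reported, Enhanced v Basic | Gap | Chi-square | Fisher |
|---|---|---|---|---|
| 50% | 0.55 v 0.55 | 0 | 6.4% | 3.2% |
| 50% | 0.65 v 0.55 | 10 points | 12.8% | 7.4% |
| 50% | 0.70 v 0.55 | 15 points | 21.3% | 13.5% |
| 30% | 0.37 v 0.37 | 0 | 5.8% | 2.7% |
| 30% | 0.51 v 0.37 | 14 points | 19.7% | 12.5% |
| 30% | 0.58 v 0.37 | 21 points | 36.3% | 26.0% |

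In the unequal rows nearly all false positives favour Enhanced (12.3 of the 12.8 points in the second row). Each rate is for one comparison at one time point.

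**Step 5: other assumptions.** Set f = 0.20 in Basic, vary t from 0.20 to 0.50, and use a normal approximation. The chance of a significant result favouring Enhanced, nominally 2.5%, becomes 5.5% to 8.3% if f = 0.30 in Enhanced, 11% to 20% if f = 0.40, and 20% to 39% if f = 0.50. A modest differential therefore does modest harm, and a large one does a lot.

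**The case against.** **The arm contrast is smaller than it looks.** Basic women also hear adherence advice: initial counseling covers it in both arms, Basic counselors meet women for three further weeks, and the doctor is to assess and support adherence at every visit (Table 1). This stands. Enhanced women still receive more, but a threefold or fourfold ratio of over-reporting has no basis in the documents.

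**There are safeguards.** The biomedical measure shares primary status and cannot be affected by how a question is asked. Medication pick-up is tracked as well. This stands and limits the point to self-report. It does not protect the self-reported primary outcome, which the plan does not subordinate to the biomarker.

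**This is a pilot for directional insight.** That reduces reliance on any one p-value. The bias, however, lies in the estimate itself: the gaps of 10 to 21 points in the table arise with no true effect.

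**Two stronger readings are not supported.** A reader might infer that follow-up interviewers do know the arm. The documents show this only at enrolment; for later interviews it is inferred from the staff category, the shared REDCap system and the absence of stated masking. A reader might also take the false-positive rates as the price of unmasked interviewers. They are not: women know what they received, and much of any differential would remain with a masked interviewer. Nothing in the documents allows the two sources to be separated.

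**Conclusion.** The concern holds in a limited form. As written, the plan leaves one of two unranked primary measures, and the self-reported secondary scales, open to over-reporting that may be greater in the Enhanced arm. It includes no comparison between arms that would reveal this. The blood or urine result is not open to this bias, so the point does not extend to the biomedical comparison.

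The size is conditional on assumed over-reporting of 30% to 40% against 10% among non-adherent women, 25 per arm and a two-sided 5% test. At 30% to 50% true adherence, false positives then run from about 13% to 36% by chi-square and 7% to 26% by Fisher, against roughly 6% and 3% with equal reporting. A smaller differential gives a smaller excess. A change is worth making because it is cheap, though the amount of bias cannot be known from the documents.

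**What to change.** 1. Keep reading the items aloud, which serves the stated literacy purpose, but let the woman enter her own answers to the adherence items, unseen by staff, on the tablet already used for REDCap consent. This is the main change, because it can also reduce over-reporting that comes from the woman knowing her own arm.
2. Hide the allocation field from the REDCap role used for follow-up surveys.
3. Where the rota allows, have follow-up done by someone other than the person who randomised her.

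The cost is minor set-up: a user-rights setting, a self-entry screen and a rota rule. It needs no extra assessor, visit or participant. Some women may make entry errors, so staff should offer help without looking at the answers. Some bias will remain because women know what they received.

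No change to question order is proposed, because the surveys are attachments that are not shown.

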HIV prevention strategies are important to address risk in WWIDs, including PrEP. HIV risk reduction strategies for WWIDs should include individual-focused strategies (e.g. negotiation skill building, condom use, HIV testing), social strategies (e.g. couple-based counseling, peer support, syringe exchange) and biomedical prevention (e.g. PrEP). PrEP medication, the latest HIV prevention tool, has been most extensively tested in men who have sex with men (MSM; e.g. iPrEX trial).⁷ With initial findings indicating significantly lower risk of HIV acquisition, subsequent studies have focused on other at-risk groups. Of those that have included women, the FEM-PrEP study⁸ (at-risk women in Africa) and the Partners PrEP³⁸ (HIV discordant couples) trial were specifically aimed at addressing risk associated with heterosexual transmission. The only trial to address IDU risk specifically occurred in Thailand involving 2,413 PWIDs.¹⁰ Results

indicated an HIV risk reduction of 48.9% in intervention PWIDs, which increased to 74% when limited only to patients with good adherence. While women overall had better PrEP adherence, there were not enough women enrolled to specifically look at barriers or facilitators to PrEP use in WWIDs. In fact, little research exists on WWIDs and their barriers to accessing and using any HIV prevention services, indicating a key area of research to stop the HIV epidemic² in this at-risk population.

Study Design

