After the appointment, PrEP medication will be delivered to Prevention Point in weekly packets. Each participant will be assigned a small locked locker and study staff will place a week's worth of medication in the locker every Monday. Participants can then pick up the medication when it's convenient for them and study staff can keep track of whether medication has been picked up. This information will be provided to the PrEP counselors so they can follow up with the participant if medication has not been picked up.

It is expected that participants will meet with their PrEP counselor at least four times during the intervention. For the “Enhanced” group, the PrEP counselor will reach out, emphasize study messages, and set up at least monthly appointments after the initial appointment. For the “Basic” group, PrEP counselors will meet with women at initial appointment and for the next three weeks. They will then be available as needed and will meet with participants when they request, but they will not actively reach out to participants which is how PrEP counseling is currently taking place. For an example of how targeted messages would be delivered in the “Enhanced” group, see table 2.

Table 2. Targeted messages for “Enhanced” group

Potential Construct from Vector Modeling	In-clinic PrEP Counseling	Written/Visual Materials	Text Message
Staying HIV- is worth taking a daily medication for.	HIV is no joke. The best way to stay HIV- is to be on PrEP. It's just one pill a day and it can significantly lower your risk of getting it.	We know you have a lot going on but if you set up a time to take the pill every day, it will get easier. We can help you think about how to add this to your day. Ask us!	Remember, it's only 1 pill a day. U can do it and we can help!
Worry about being able to take medication every day	It can be a pain to take medication every day but it's worth the effort because you can be sure that you stay free from HIV.	You may not want to take medication every day because of the time and effort it takes. But it is worth it. It can give you the peace of mind to know that you are HIV free.	Get peace of mind! Take your medication every day. Call XXX-XXX-XXXX if you have ??

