Worry that taking medication will interfere with drug use.	I know you might worry that taking PrEP might interfere with your daily life, especially if you are	There is no evidence that taking PrEP will interfere with taking other substances.	Getting your medication is easy and doesn't interfere with other use.

	using substances. But there is no reason to worry. PrEP is safe and easy to take and because you are getting it here at Prevention Point, it is easy to talk.		Call XXX_XXX_XXX if you have ?s!
Don't believe doctors will want to treat WWIDs or care about them staying HIV-	I know sometimes it's hard to go to the doctor, but we have doctors who really care about our clients and who want you to stay HIV negative.	Some people do not like to go to the doctor, but using PrEP can help you stay HIV-. We only send our clients to doctors we know will work with you and who care about your health.	Remember...UR doc wants you to keep taking your medication every day! Call XXX-XXX-XXXX if you have ??

All participants will receive study text messages throughout the study. “Enhanced” group participants will receive weekly text messages. These texts will include supportive messages about taking PrEP that emphasize why they should continue to take their PrEP as prescribed, as well as reminders to pick up their medication. “Basic” group participants will receive bi-monthly text message reminders to pick up their medication. We will work with Mosio, which provides text messaging services and has experience working with studies funded by the National Institutes of Health. Temple University has signed a contract with Mosio for this service. In that contract is a data sharing agreement that states that any data collected for the study will be shared with [name], the Principal Investigator, and cannot be used for any other purpose.

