Participants will also continue to be monitored by the physician at Prevention Point. It is expected that a blood test or urine sample measuring PrEP levels and an HIV screening test would be done at the beginning, mid-point and the end of the intervention. It will also be done three months after the intervention is over. This will provide biomedical adherence data and ensure that participants have remained HIV negative.

After the intervention is over, all study participants may continue their PrEP prescription and have it administered out of the medical clinic at Prevention Point. In addition, PrEP counselors will remain available for participants should they have any further questions. Specialized counseling and text messages will no longer be provided. Three months after the intervention is over, we will contact participants to complete the last study assessment. This will be done at Prevention Point when the participant is there.

Instruments

There are five study assessments (See attachments). They include:

1. Eligibility Screener
2. Baseline Assessment
3. Mid-Intervention Assessment (in person and one question via text)
4. Post-Intervention Assessment
5. Three month follow-up Assessment

Analysis Plan

General - All data will be graphed and tabulated by treatment group for review of distributional properties and anomalous values prior to the main analyses. Continuous and normally distributed variables will be summarized with means and standard deviations. All parameter estimates will be bound by 95% confidence intervals and tests for differences in means and proportions will be deemed statistically significant $p < 0.05$. Post-hoc tests of significance will be based on adjustments for alpha to protect family-wise error rates at 5% using the method of Benjamini & Hochberg. For all analyses described in this study, we will use Statistical Analysis Software (SAS, version 9.4, Cary, N.C.).

Primary Outcome. The study's intent is to provide directional insight into the design of subsequent programmatic studies. As such, univariate group comparisons will be accomplished using an independent two-sample t-test for continuous measures (or non-parametric Wilcoxon

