Participation may contribute to increasing participants' initiation and adherence of PrEP, which will lower their HIV risk. Participation also may help participants consider how perceived stigma impacts their feelings about PrEP and help "normalize" the use of HIV prevention within the IDU community. The risks of discomfort or embarrassment discussing HIV and PrEP are reasonable in relation to the anticipated direct benefits to the subjects and the contribution subjects can make to society by reducing HIV stigma among WWIDs and encouraging HIV prevention efforts among their peers.

Privacy

As noted, all data will be coded to protect the confidentiality of participants. Only the Principal Investigator and the study coordinator will have access to the list of actual participant names and cell phone numbers. That list will be kept in a locked file (hardcopy only) in the office of [name]. The REDCap dataset with the coded data, with names removed, will be stored behind the firewall of Temple University. Medical information (adherence, HIV tests etc.) in medical charts will not be removed from Prevention Point. The study coordinator will access this through Prevention Point's electronic health record and note findings in the de-identified REDCap

database that will assign an ID number for each participant. Information will be entered into REDCap as coded data (i.e. adherence is coded 0 as no, 1 as yes). The PrEP counselors will know the names of the participants, but they will not have access to the REDCap database or participant medical records. The research assistant will only have access to de-identified data.

Compensation

Participants will receive up to a total of \$175 in gift cards. These incentives will be provided for different steps of the research study. Compensation will not be provided to those who drop out of the study or do not complete the step. Compensation will be broken down as follows:

- \$5 for conducting the eligibility screener and HIV test
- \$15 for completing the baseline test
- \$40 for meeting with the PrEP counselor (Up to four times, \$10 each time)
- \$15 for doctor visits (three times, \$5 each time)
- \$10 for completing one-month survey
- \$20 for completing three month survey
- \$50 for completing three month follow up survey
- \$20 for cell phone minutes

References

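### An example Enhanced-arm counselling message in Table 2 promises certain protection from HIV, which nothing in the protocol supports

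*Combined protocol and SAP*

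**What the plan says.** The Procedure section introduces Table 2 with the words "For an example of how targeted messages would be delivered in the" Enhanced group. The table has four constructs, each with an in-clinic counselling message, a written or visual message, and a text message. The second construct is worry about taking a medication every day. Its counselling cell concedes that daily pills are a nuisance and says they are worth it "because you can be sure that you stay free from HIV".

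Other parts of the protocol put the benefit differently:

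- Table 2, row 1, counselling: of a once-daily pill, "it can significantly lower your risk of getting it".
- Table 2, row 4, written material: "using PrEP can help you stay HIV" negative.
- Potential Benefits to Participants: taking part may increase "initiation and adherence of PrEP, which will lower their HIV risk".
- Background, on the one cited trial in people who inject drugs: results "indicated an HIV risk reduction of 48.9% in intervention PWIDs, which increased to 74% when limited only to patients with good adherence".

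The SAP does not address message content.

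**The concern.** The row 2 clause looks ahead (staying free of HIV), asserts certainty, and gives that certainty as the reason for taking the pill. It contains no word such as *help* or *lower*, and it does not mention testing, so it is hard to read as a remark about current tested status.

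The women who would hear it are enrolled because they report sharing needles or having unprotected sex in the last 3 months (Inclusion Criteria, item 3). If the sentence is used as written, women with recent exposure risk are told something about their protection that the protocol cannot back up. What is at stake is the accuracy of health information given to participants. No effect on precautions, outcomes, analysis or sample size is claimed.

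**Working it through.** The plan has no statistical figure to reproduce on this point. The check compares the clause with what the documents say about protection, and then counts how much of Table 2 is affected.

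**1. Does any cited figure support certainty?** Certain protection would mean a 100% risk reduction. The Background gives two figures for people who inject drugs:

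| Cited risk reduction | Shortfall from 100% |
|---|---|
| 48.9% overall | 100 − 48.9 = 51.1 percentage points |
| 74% with good adherence | 100 − 74 = 26 percentage points |

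These figures are not a like-for-like comparator. The protocol does not define good adherence as daily dosing. The reference list shows that the cited trial studied tenofovir, whereas Table 1 has the physician prescribe Truvada. The shortfalls therefore do not estimate the risk left to these participants. They show only that the cited evidence stops short of certainty. For other populations the Background speaks of lower risk, and nowhere do the documents report complete protection.

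**2. Does assuming daily use rescue the clause?** No. Row 1 also describes a once-daily pill, and its claim is that "it can significantly lower your risk of getting it". With the same regimen in the same counselling column, one row claims reduced risk and the next claims certainty.

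**3. Is the clause in line with the other statements of benefit?** Row 4 speaks of help, and Potential Benefits speaks of lowered risk. Row 2 counselling goes further than either.

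**4. How much text is affected?** 4 rows × 3 delivery columns = 12 message cells. The clause appears in 1 of the 4 counselling cells, which is 1 of the 12 cells overall. The row 2 written text, about the peace of mind of knowing one is HIV free, is not counted because it can be read as referring to tested status.

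**5. How many women would hear it?** This cannot be derived. The documents do not contain the final counselling script or say how often any one message is used.

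The planned repeat HIV screening, meant to "ensure that participants have remained HIV negative", is not used as evidence here. Imperfect adherence would explain it equally well.

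**The case against.** The strongest reply is that this is sample copy. Table 2 is offered as an example, its first column lists potential constructs, and its text-message cells still hold placeholder phone numbers. Nothing shows that the sentence is final. This stands, and it is the main reason the point is minor. But Table 2 is the only message wording in the documents, and the Enhanced counsellor is told to emphasise the study messages, so a faulty model sentence is best corrected before scripts are written from it.

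Second, the phrase is colloquial and could be heard as *make sure you stay negative*. That reading is possible, but the literal one is more natural, and participants should not have to choose between them.

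Third, other contacts cover the ground. Table 1 lists risk-reduction counselling at the first visit and, for all visits, "Assessment of STI symptoms, HIV risk behavior, counseling for risk reduction". Safe sex and drug use information is given to all women at consent (Risk to Participants, item 5). These lessen any harm but do not make the sentence accurate. The physician does not know the participant's group, so that counselling cannot be aimed at women who heard this message. The study consent (Attachment D) and the medication fact sheet were not available and may state the limits of protection. Nothing is assumed about them.

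Fourth, row 1 also calls PrEP the best way to stay negative. That is a superlative, not a promise of certainty, so the contrast between the rows holds.

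**Conclusion.** The concern holds as a minor point. The row 2 counselling example promises certain protection, and no statement or figure in the documents supports that. Its extent is one clause in one example cell.

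The conclusion rests on the natural reading of the clause and on the absence of any claim of complete protection in the documents. It does not depend on treating 48.9% or 74% as the protection these women would get. Exposure and harm are unknown.

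**What to change.** Replace the row 2 counselling clause with a risk-lowering reason in line with row 1, for example: *because taking it every day can greatly cut your chance of getting HIV*. When the Enhanced scripts, print materials and text messages are finalised, confirm that none promises certain protection. Rewording the row 2 written text is optional.

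The cost is one clause and a slightly less emphatic motivational message that sits closer to row 1. Allocation, outcomes, analysis and sample size are untouched.
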